Sponsor may elect to close an arm, the enrollment or study procedures for other arms of the study will remain unaffected. In addition, there are no current plans to add more cohorts or to expand the existing cohorts in this study. At implementation of Amendment 05, the following treatment arms are considered closed: Cohort B: MK-4280A, Cohort B: MK-7684A, and Cohort B: MK-4830+pembrolizumab.

As of the Investigator Letter dated 16-DEC-2024, participants who were receiving MK-4280A were offered the option to continue study therapy until treatment completion or transition to pembrolizumab monotherapy, and participants who were receiving MK-7684A were discontinued from that study therapy and offered the option to transition to pembrolizumab monotherapy. As per the Investigator Letter dated 25-SEP-2023, the MK-4830+pembrolizumab arm was closed to enrollment; all ongoing participants were offered the option to continue study therapy until treatment completion or transition to pembrolizumab monotherapy.

Participants who opt to continue treatment with pembrolizumab monotherapy will remain on the same visit schedule as per the initial assignment.

Participants in closed arms with access to approved SOC (eg, immunotherapy, chemotherapy, targeted therapy) should be considered for discontinuation from the study. Participants in closed arms who are benefiting from pembrolizumab monotherapy, but unable to access it as SOC outside the study, may continue on study and receive treatment with pembrolizumab monotherapy until discontinuation criteria are met. The final required study visit will be the Safety Follow-up Visit.

Participants will be evaluated with tumor scans and RECIST 1.1 response assessment (chest, abdomen, and pelvis) Q9W (63 ± 7 days) from the date of allocation until disease progression is assessed by the site and verified by BICR or initiation of a new anticancer treatment. All scans obtained will be assessed by the BICR using RECIST 1.1 for determination of ORR and PFS. Refer to Section 8.2.1 for imaging information for participants in closed arms.

Survival follow-up will continue after disease progression is verified by BICR or the start of new anticancer treatment for participants in open arms. In addition, upon Sponsor request, participants may be contacted for survival status at any time during the study. Refer to Section 8.11.4 for posttreatment follow-up information for participants in closed arms.

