Discontinuation of study treatment may be considered for participants who achieve CR per RECIST 1.1 by 2 tumor scans at least 4 weeks apart, were treated with at least 4 cycles (if dosed Q6W) or 8 cycles (if dosed Q3W) of study intervention before discontinuing treatment and received at least 1 treatment (Q6W) or 2 treatments (Q3W) beyond the date when the initial CR was declared.

Participants who stop study intervention after a CR and who later progress, and participants who show PR or SD throughout the first 2 years of treatment and who progress after completing therapy may be eligible for the Second Course Phase. Refer to Section 6.1.1.2 for additional details and for Second Course treatment information for participants in closed arms.

Participants may undergo resection of the primary tumor and/or metastasectomy with curative intent after achieving a response to study intervention that converts previously unresectable disease to resectable disease, if deemed eligible per investigator's discretion in a multidisciplinary approach according to his/her institutional standard, and with Sponsor consultation. After surgery, when clinically appropriate and after the surgical wound is fully healed, the participant may resume the same therapy they were receiving pre-operatively starting at least 4 weeks and no more than 12 weeks post-surgery, unless approved by the Sponsor.

Post-operative therapy may continue until verified progression by BICR, intolerability, or completion of the assigned number of cycles of treatment (as per study arm).

The first post-operative tumor scan should be performed at a minimum of 4 weeks after surgery and no more than 8 weeks after surgery and before the start of the next treatment cycle (Section 8.2.1.2). If treatment does not resume within 12 weeks after surgery, the investigator should consult with the Sponsor. In addition, participants who discontinue study intervention for reasons other than radiographic disease progression will have posttreatment follow-up for disease status Q9W (± 7 days) from date of randomization until disease progression (verified in an expedited manner by BICR, for participants in open arms, per RECIST 1.1), start of a non-study anticancer therapy, consent withdrawal, becoming lost to follow-up, death, or end of the study, whichever occurs first.

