8.2.1.2 Tumor Scans During the Study

The first on-study scan should be performed at 9 weeks (63 days \pm 7 days) from the date of allocation. Subsequent tumor scans should be performed every 9 weeks (63 days \pm 7 days) or more frequently if clinically indicated. Scan timing should follow calendar days and should not be adjusted for delays in cycle starts.

Scans are to be performed until disease progression is identified by the investigator and verified by the BICR, for participants in open arms, or until the start of new anticancer treatment, withdrawal of consent, or death, whichever occurs first.

Objective response should be confirmed by a repeat scan performed at least 4 weeks after the first indication of a response is observed. Participants will then return to the regular scan schedule, starting with the next scheduled time point. Participants who receive additional scans for confirmation do not need to undergo the next scheduled scan if it is fewer than 4 weeks later; scans may resume at the subsequent scheduled time point.

On-study brain or bone scans should be performed if clinically indicated or to confirm CR (if other lesions indicate CR and brain or bone lesions existed at baseline).

For participants who have surgery with curative intent during the study, scans must be performed at a minimum of no less than 4 weeks after surgery and no more than 8 weeks prior to the next treatment cycle. The last set of scans prior to restart of treatment will be used to establish a new baseline of tumor burden. Subsequent scans will be compared to this new baseline and the visit responses will be limited to PD, non-PD, or NE (not evaluable); these new post-operative images will be assessed every 9 weeks (63 days \pm 7 days) from the

new baseline scan date until disease progression is assessed by the site and verified by BICR or initiation of a new anticancer treatment.

While off study intervention, participants who undergo surgical resection of visible disease may demonstrate disease progression in non-surgical sites. In this instance, disease progression might not necessarily reflect resistance to study intervention. Accordingly, participants who develop isolated lesion/tumor growth post-operatively (eg, while off study intervention) may resume the previously assigned study intervention. The investigator must assess overall clinical benefit to the participant and consult the Sponsor prior to resuming study intervention.

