9.4.1 Efficacy Endpoints

Primary

- **Objective Response Rate**

The ORR is defined as the percentage of participants who achieve a confirmed CR or PR per RECIST 1.1 as assessed by BICR.

Secondary

- **Duration of Response**

For participants who demonstrate confirmed CR or PR, duration of response is defined as the time from the first documented evidence of CR or PR until disease progression or death due to any cause, whichever occurs first.

- **Progression-Free Survival**

The PFS is defined as the time from randomization to the first documented disease progression per RECIST 1.1 or death due to any cause, whichever occurs first.

- **Overall Survival**

OS is defined as the time from randomization to death due to any cause.

- **Objective Response Rate**

The ORR is defined as the percentage of participants who achieve a confirmed CR or PR per RECIST 1.1 as assessed by the investigator.

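### After curative-intent surgery, section 8.2.1.2 resets the tumour baseline while the SAP counts the first BICR progression, so PFS and DOR events in operated responders may be lost or delayed

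*Combined protocol and SAP*

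**What the plan says.** **Who has surgery.** Section 4.1 allows resection with curative intent "after achieving a response to study intervention that converts previously unresectable disease to resectable disease". It is at the investigator's discretion, with multidisciplinary input and Sponsor consultation, in an open-label trial. Afterwards "the participant may resume the same therapy they were receiving pre-operatively starting at least 4 weeks and no more than 12 weeks post-surgery", unless the Sponsor approves otherwise.

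**How scans are then read.** Section 8.2.1.2: "The last set of scans prior to restart of treatment will be used to establish a new baseline of tumor burden". Later scans are compared with that baseline and can be called only progression, no progression or not evaluable. The section recognises that disease outside the operated sites may progress while the participant is off treatment, and that "participants who develop isolated lesion/tumor growth post-operatively (eg, while off study intervention) may resume the previously assigned study intervention".

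**How events are defined.** Section 9.4.1: "The PFS is defined as the time from randomization to the first documented disease progression per RECIST 1.1", or death. Section 9.6.1.3 dates a progression at the first assessment where BICR documents it. DOR runs from first response to progression or death. Tables 9 and 10 have no row for surgery or for a new baseline.

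**Scan timing.** Section 4.1 puts the first post-operative scan at least 4 weeks and "no more than 8 weeks after surgery and before the start of the next treatment cycle". Section 8.2.1.2 puts it at least 4 weeks after surgery and "no more than 8 weeks prior to the next treatment cycle". Section 4.1 runs nine-weekly scans "from the date of allocation until disease progression is assessed by the site and verified by BICR"; section 8.2.1.2 counts the nine weeks from the new baseline scan for operated participants.

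**The concern.** RECIST progression is normally judged against the smallest tumour burden reached. If the scan just before restart becomes the reference, growth in unresected lesions or a new lesion that appeared since the pre-operative nadir is built into that reference. A participant whose disease progressed off treatment could then be event-free until it grows again from the higher level.

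One such participant could be handled in three ways: as an event on the post-operative scan (section 9.6.1.3), as a later event or none (section 8.2.1.2), or as censored before surgery if resection counts as new anticancer therapy, which the plan does not settle. Two secondary endpoints would then depend on a choice made after the data are seen.

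Only responders can enter this pathway, so an arm with more responses can have more reset baselines. This still matters for MK-1308A against pembrolizumab in both cohorts. The other three Cohort B arms are closed and no longer read by BICR.

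**Working it through.** The plan gives no surgery rate and no count of re-baselined participants, and its cohort sizes are redacted. There is no figure to reproduce, so the effect is bounded by assumption.

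**1. The mechanism.** Assume progression means 20% above the reference sum (the documents do not state the threshold). Take a nadir of 50 mm in unresected lesions and 65 mm on the pre-restart scan.
- Against the nadir: 65/50 − 1 = 30%, above the threshold of 1.2 × 50 = 60 mm, so progression.
- After the reset: the next progression needs 1.2 × 65 = 78 mm.

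**2. Masked events per arm.** Masked = ORR × s × g, where s is the share of responders who have surgery and restart (assumed 5% to 30%) and g is the share of those with growth that would be progression against the nadir (assumed 10% to 50%). ORR is 44% and 62%, the illustrative rates in section 2.3; the 62% comes from another PD-1/CTLA-4 doublet.

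| s, g | per 100, ORR 44% | per 100, ORR 62% | per arm of 45 |
|---|---|---|---|
| 5%, 10% | 0.22 | 0.31 | 0.1 vs 0.1 |
| 10%, 30% | 1.32 | 1.86 | 0.6 vs 0.8 |
| 30%, 50% | 6.60 | 9.30 | 3.0 vs 4.2 |

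An arm of about 45 is 320/7, assuming equal arms. With the same s and g in both arms, the higher-response arm holds 0.62/(0.44 + 0.62) = 58% of masked events, or 0.62/0.44 = 1.4 times the other arm's.

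**3. Effect on the PFS hazard ratio.** A Cox model was fitted to 200,000 simulated participants per arm. Assumptions: median PFS 48 months in responders and 4 in non-responders, 36 months of follow-up, growth seen at month 9. Both ratios in each cell come from the same simulated participants, first with the month-9 event counted, then masked.

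| s, g | found later, median 6 months | found later, median 24 months | never found |
|---|---|---|---|
| 10%, 30% | 0.731 → 0.729 | 0.733 → 0.729 | 0.732 → 0.725 |
| 20%, 30% | 0.736 → 0.734 | 0.733 → 0.725 | 0.739 → 0.724 |
| 30%, 50% | 0.750 → 0.742 | 0.747 → 0.727 | 0.753 → 0.718 |

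The shift runs from 0.002 to 0.035. With ORR 44% in both arms the ratio stays at about 1.00 either way. Twelve-month PFS rises by about 1 to 2 points within arms at s = 10%, g = 30%, and by 4 to 8 points at s = 30%, g = 50%.

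**4. The scan windows.** Suppose treatment restarts at week 12. Section 4.1 asks for the first post-operative scan in weeks 4 to 8. Section 8.2.1.2 reaches back 12 − 8 = 4 weeks after surgery, so it accepts a scan anywhere in weeks 4 to 12. A single scan at week 11 meets the second and fails the first. For any restart by week 12, the 8-week limit in section 8.2.1.2 adds nothing to its own 4-week minimum.

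**5. The calendar.** The rule in Tables 9 and 10 for two or more missed assessments needs a defined schedule. For operated participants the plan gives two starting points, allocation and the new baseline scan, and does not say which one the censoring rule uses.

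**The case against.** The strongest reply is that nothing is lost. Section 4.1 has BICR assess all scans for PFS, section 9.6.1.3 counts the first progression BICR documents, and the reset in section 8.2.1.2 governs only scans after the new baseline. Being allowed to restart does not mean that an event goes uncounted, since section 7.1 already separates treatment beyond progression from the PFS event. This stands as one available reading, and it is why the point is a conflict and not a proven loss. It does not settle the matter. Section 8.2.1.2 does not say which reference applies to the pre-restart scan, and it continues central assessment until BICR verifies progression, with no exception for participants who have already grown. Section 8.2.1.5 stops sending scans centrally once progression is verified.

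A reader might infer that events are lost mostly in the arm with more responders, or take a crude event ratio such as 17/20 = 0.85 as the hazard-ratio bias. The documents support neither. The crude ratio assumes 20 events in the arm, three of them lost for good, and none lost in the comparator. Both arms have operated responders, and later growth or death is still an event. Even the most extreme case above gives 0.718/0.753 = 0.95. The 58% share also needs equal surgery rates among responders.

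A reader might likewise infer between-arm bias in DOR. DOR is analysed in responders only, by Kaplan-Meier, with no between-arm test; at equal surgery rates it is inflated by a similar fraction in each arm.

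On timing, the window in section 4.1 is for the first post-operative scan and the baseline in section 8.2.1.2 is the last one before restart, so both limits can be met together. The restarted clock is an express rule that keeps the nine-week interval. The wording still needs aligning.

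**Conclusion.** The point holds as an unresolved conflict between section 8.2.1.2 and sections 9.4.1, 9.6.1.2 and 9.6.1.3. PFS and DOR events in responders who have surgery and restart may be lost or delayed, and PFS is affected somewhat more often in the arm with the higher ORR. The case rests on having one event definition, not on a large expected bias: the shift in the PFS hazard ratio is small unless surgery among responders is common. The surgery and growth rates, arm sizes, PFS medians and 20% threshold behind these figures are all assumptions. Primary ORR is not affected, because post-operative visits cannot be read as a response. The two scan windows and two calendars are separate inconsistencies that must be reconciled.

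**What to change.** - In sections 8.2.1.2, 9.6.1.2 and 9.6.1.3, state that for PFS and DOR the BICR reads every scan between surgery and restart against the pre-operative nadir of unresected lesions. A progression there is an event on that scan date, whether or not treatment resumes. The new baseline is used only after a post-operative scan without progression.
- State whether resection counts as new anticancer therapy under Tables 9 and 10. If it does, participants are censored before surgery and the rule above cannot operate, so the two statements must agree.
- Add a sensitivity analysis that censors PFS and DOR at surgery, and report the number of surgeries by arm.
- Reconcile the post-operative scan windows in sections 4.1 and 8.2.1.2, and the scan calendar (allocation or new baseline). Say which calendar defines a missed assessment.

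The cost is wording in the protocol, the SAP and the instructions to central readers, plus one extra analysis. The analysis rules can go in the supplemental SAP that section 9 provides for. The downside is a few more PFS and DOR events among operated responders.

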8.2.1.3 End-of-treatment and Follow-up Tumor Scans

If participants discontinue study intervention, tumor scans should be performed at the time of discontinuation (± 4 -week window) unless previous scans were obtained within 4 weeks of discontinuation. If participants discontinue study intervention due to documented disease progression, this is the final required tumor scan.

If participants discontinue study intervention without documented disease progression, every effort is to be made to monitor disease status by acquiring tumor scans using the same schedule calculated from the date of allocation (refer to Section 8.2.1.2).

Scans are to be continued until one of the following conditions are met:

- disease progression as defined by RECIST 1.1 verified by BICR
- the start of a new anticancer treatment
- pregnancy
- death
- withdrawal of consent
- the end of the study

Refer to Section 8.11.4 for posttreatment follow-up information for participants in closed arms.

8.2.1.4 Second Course (Retreatment) Tumor Scans

Tumor scans must be performed within 28 days before restarting study intervention.

If disease progression has been verified by BICR (required only for participants in open arms) for the First Course, the Second Course may be initiated. The disease progression scan may be used as the Second Course baseline scan if performed within 4 weeks prior to dosing and meets scan standards.

The first scan should be performed at 9 weeks (63 days \pm 7 days) after restarting study intervention. Subsequent tumor scans are to be performed every 9 weeks (63 days \pm 7 days) or more frequently, if clinically indicated.

Scans are to be performed until disease progression, the start of a new anticancer treatment, withdrawal of consent, death, completion of Second Course or notification by the Sponsor, whichever occurs first.

If participants discontinue study intervention, tumor scans are to be performed at discontinuation (\pm 4 week window) unless previous scans were obtained within 4 weeks of discontinuation. If participants discontinue study intervention due to documented disease progression, this is the final required tumor scan.

If participants discontinue study intervention without documented disease progression, every effort is to be made to monitor disease status by acquiring tumor scans every 9 weeks (63 days \pm 7 days) until either the start of a new anticancer treatment, disease progression, death, or the end of the study, whichever occurs first.

Response assessments and progressive disease are determined by investigator assessment.

The only Second Course scan to be provided to the iCRO is the baseline scan if it is the final scan for the Initial Treatment or First Course.

Refer to Section 8.2.1 for imaging information for participants in closed arms.

8.2.1.5 RECIST 1.1 Assessment of Disease

RECIST 1.1 will be used as the primary measure for assessment of tumor response, date of disease progression, and as a basis for all protocol guidelines related to disease status (eg, discontinuation of study intervention). Although RECIST 1.1 references a maximum of 5 target lesions in total and 2 per organ, this protocol allows a maximum of 10 target lesions in total and 5 per organ, if clinically relevant to enable a broader sampling of tumor burden.

Upon investigator-assessed disease progression, for participants in open arms, the indicative scans are to be submitted immediately to iCRO for BICR verification of progression. After submission of scan(s), the iCRO will email the assessment to the site and Sponsor.

If disease progression is not verified, the process continues as follows:

- If participant is clinically stable, continue study intervention per protocol
 - resume imaging per protocol schedule (\geq 4 weeks to next scan)
 - send scans to iCRO
 - continue local assessment
 - do not change investigator assessment of progression

- if subsequent scan(s) indicate progression, submit scan(s) to iCRO to request verification
- If the participant is not clinically stable, best medical practice is to be applied

Before stopping study intervention or imaging or starting new anticancer therapy in a participant who is clinically stable, communication with the Sponsor is required.

If disease progression is verified, the process continues as follows:

- investigator judgement will determine action
- if the participant is clinically stable and study intervention is to continue, communication with the Sponsor is required and a reconsent addendum must be signed
- obtain scans locally per original protocol schedule
- do not send scans to iCRO

[figure not shown]
Figure 2 illustrates the study intervention decision process involving verification of disease progression for participants.

- For the purpose of this decision process, lack of clinical stability is defined as:
 - unacceptable toxicity
 - clinical signs or symptoms indicating clinically significant disease progression
 - decline in performance status
 - rapid disease progression or threat to vital organs or critical anatomical sites (eg, CNS metastasis, respiratory failure due to tumor compression, spinal cord compression) requiring urgent alternative medical intervention

Refer to Section 8.2.1 for imaging information for participants in closed arms.

Figure 2 Study Intervention Decision Making Process When Progression per RECIST 1.1 is Observed by Investigator (PFS Endpoint)

Study Intervention Decision Making Process When Progression per RECIST 1.1 is Observed by Investigator (PFS endpoint)

iCRO=imaging Contract Research Organization; VOP=verification of progression

8.2.2 Patient-reported Outcomes

CCI

[Redacted text block]

8.3 Safety Assessments

Details regarding specific safety procedures/assessments to be performed in this study are provided. The total amount of blood/tissue to be drawn/collected over the course of the study (from prestudy to poststudy visits), including approximate blood/tissue volumes

drawn/collected by visit and by sample type per participant, can be found in the Laboratory Manual or Procedure Document.

Planned time points for all safety assessments are provided in the SoA.

Participants in closed arms who complete study treatment (including Second Course, if applicable) or otherwise meet EOT criteria will be discontinued from the study after the EOT visit and any required Safety Follow-up Visit.

Participants in closed arms remaining on study should continue to be monitored in the study through the AE reporting period (Section 8.4).

